**Table 5. Simulation scenarios.**

		Treatment			
		1	2	3	4
Scenario 1	Pr(Quit)	0.2	0.2	0.2	0.2
Eff: No Difference	Pr(Efficacy)	0.3	0.3	0.3	0.3
Quit: No Difference	Utility	1.025	1.025	1.025	1.025
Scenario 2	Pr(Quit)	0.3	0.25	0.15	0.3
Eff: Best and 2 nd Best	Pr(Efficacy)	0.3	0.4	0.5	0.3
Quit: Positive	Utility	0.925	1.050	1.225	0.925
Scenario 3	Pr(Quit)	0.3	0.25	0.15	0.3
Eff: One Strong Best	Pr(Efficacy)	0.3	0.3	0.5	0.3
Quit: Positive	Utility	0.925	0.975	1.225	0.925
Scenario 4	Pr(Quit)	0.2	0.4	0.4	0.2
Eff: One Strong Best	Pr(Efficacy)	0.3	0.3	0.5	0.3
Quit: Negative	Utility	1.025	0.825	0.975	1.025

**Table 6. Simulated Trial Operating Characteristics.**

Scenario	Prob. Success	Prob. Early Success	Mean Trial Weeks	Mean Patients				
				Total	T1	T2	T3	T4
1 (No Difference)	0.061	0.055	108	393	99	99	97	99
2 (Best & 2nd Best+)	0.798	0.777	78	298	51	80	116	52
3 (One Strong Best+)	0.939	0.923	68	266	51	58	105	51
4 (One Strong Best-)	0.115	0.103	107	387	108	62	107	109

Prob. Drug Wins

Prob. Drug

Scenario	Pr(Treatj Best)>.925				Loses Pr(Treatj Best<.01)			
	T1	T2	T3	T4	T1	T2	T3	T4
1 (No Difference)	0.015	0.015	0.014	0.017	0.075	0.064	0.088	0.068
2 (Best & 2nd Best+)	0.000	0.001	0.797	0.000	0.744	0.238	0.000	0.736
3 (One Strong Best+)	0.000	0.000	0.939	0.000	0.661	0.461	0.000	0.682
4 (One Strong Best-)	0.053	0.000	0.011	0.051	0.030	0.647	0.104	0.034

NOTE: For Quit, "positive" means quit percentages are low and "negative" means quit percentages are high

### Secondary Endpoints

The previous discussion focused on our primary endpoints, efficacy and quit rates. The temporal patterns of our secondary endpoints, SF-12, pain interference, fatigue, and sleep disturbance, will be longitudinally modeled using a two-level (time, patient) hierarchical linear modeling approach to evaluate these variables within each arm across time .

[figure not shown]

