**A. Abstract:**

Peripheral Neuropathy affects over 20 million Americans. Some neuropathies are secondary to readily identifiable causes, with diabetic sensory polyneuropathy being the most common cause in the United States. Once known causes are excluded, approximately 25 to 50% remain idiopathic and are referred to as cryptogenic sensory polyneuropathy (CSPN). This usually affects people over the age of 50. Neuropathic pain is a presenting symptom in 70-80% of CSPN. According to a poll obtained by the Neuropathy Association, 87% of patients rated pain management as the most challenging in managing their neuropathy. Currently there have been no prospective trials performed in the large CSPN group.

The overall objective of this trial is to determine which pharmaceutical therapy is most effective and causes the fewest side effects in CSPN. To do this comparative effectiveness study, we will use an adaptive design model.

**Specific Aim 1:** Determine which drug is most effective in producing pain relief and improving quality of life in patients with CSPN. We will perform a prospective randomized comparative effectiveness adaptive design study in neuropathy patients with pain who do not have diabetes and for whom no other cause has been found. The four drugs we will use are nortriptyline, duloxetine, pregabalin and mexiletine.

**Specific Aim 2:** Determine which drug has the fewest and which has the most side effects. We will use the MedDRA adverse event coding system and the number of dropouts due to side effects.

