Most randomized, controlled pharmacologic studies in neuropathic pain have evaluated antidepressants and anticonvulsants. Prospective randomized controlled clinical trials in neuropathic pain using placebos share a number of challenges and shortcomings. The response to placebo is considerable, typically observed in one-third  and at times in more than one-half of patients . Although statistically significant differences may be demonstrated between active treatment and placebo groups, the actual clinical benefit of a 1- or 2-point drop on an 11-point Likert-type scale for pain intensity is debatable. And, although they provide objective data, neurophysiologic outcome measurements have not been helpful .

Another consideration for U.S. clinicians is that labeled indications in the U.S. are limited to duloxetine and pregabalin for painful diabetic neuropathy; carbamazepine for trigeminal neuralgia; and gabapentin, pregabalin, lidocaine, and high-dose capsaicin patches for postherpetic neuralgia. Some countries permit more liberal indications that cover neuropathic pain in general, whereas others require labeling for only specific forms of painful neuropathy . In the United States this seems to vary based on the insurance carriers. Some carriers deny the use of a neuropathic pain drug if it is not one of the two FDA approved drugs for diabetic neuropathy patients.

For this study, we will use two drugs that are FDA approved for diabetic peripheral neuropathy (**pregabalin** and **duloxetine**) and two drugs (**mexiletine** and **nortriptyline**) that are often used in U.S. clinics to treat painful peripheral neuropathy. We will not use a placebo group in this comparative effectiveness study. Below we discuss these drugs; further rationale for choosing these is provided under Criterion 3.

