### Choice of Outcomes

Patients will complete a Likert-type scale for pain, the PROMIS 6 item pain interference scale, the SF-12, and the PROMIS fatigue and sleep disturbance scales. The first endpoint, or outcome, is a patient responder-defined measure of efficacy (i.e., if the patient reports a pain score at the end of 12 weeks that is 50% or greater from what they reported when they started the study, then it is efficacious for that patient). The second endpoint is the percentage of patients who discontinue treatment. Our secondary endpoints, SF-12, pain interference, fatigue, and sleep disturbance, also will be longitudinally modeled (see content after Table 5.)

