## **D. Analytic Methods**

### Overview

The primary aim of this study is to determine which drug is most effective and most tolerable in producing pain relief. We will perform a prospective randomized comparative effectiveness adaptive design study with those who do not have diabetes and in whom no other cause for neuropathy has been found. We have an agreement from 40 sites to participate in the study and four drugs will be tested. In this design we will perform several interim analyses (interims) while controlling the overall Type I error rate.

The following sections focus on specific details of this design and detail how we determined power, sample size, and duration of this trial. Throughout we add information to help those less familiar with our design and analyses better understand what we did and plan to do with this study.

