### Bayesian Adaptive Design

Patients will be randomized to one of four treatment arms (groups) with a maximum number of patients  $n_{max}=400$ . Using a Bayesian Adaptive Design, at each interim analysis a decision will be made to either continue enrolling patients or to stop the trial for success. If patient enrollment continues, the randomization structure (i.e., how we randomize patients to each drug) will also be updated. Two endpoints are used to drive the adaptive randomization and stopping criteria. The first endpoint is the percentage of patients who report a 50% or greater decrease on the Likert-type pain scale after 12 weeks. The second endpoint is the percentage of patients that discontinue treatment. After 80 patients are enrolled (see definition of “enrolled” in the consent form section towards the end of this protocol) and equally randomized to the four arms, we begin adapting the randomization. Then, after we have endpoint data on 100 patients, the data will be analyzed (a first interim analysis) and an updated randomization schedule will be used. Specifically, the arm, or drug, that looks to be the best

will get more participants allocated to it in this subsequent randomization. A new adaptive randomization schedule will be updated and an interim analysis will occur every 13 weeks after the first interim analysis, using up to date outcome data, until the trial is stopped (i.e. for early success). Early success stopping criteria will be if the probability of the maximum arm (i.e., the best drug), measured by a combined utility of the pain and treatment discontinuation endpoints, is larger than 0.925. While this will halt new patient enrollment, we will confirm this finding with a subsequent analysis and evaluation after all data from all enrolled patients are obtained as some will still be actively in the study when the early stopping criterion is identified. Also determined is which of the arms are losers, and is defined as an arm that has a probability of being maximum as less than 0.01. This will be a useful result in cases where a best arm could not be identified. If a loser or two is identified then the drug(s) would not be recommended for use in clinical practice.

A summary of the overall general design is as follows.

- Begin a new adaptive randomization schedule once 20 patients have been enrolled on each treatment.

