#### Adaptive Randomization: Allocation

After the stopping rule is evaluated the next round of patients are randomized using a formula that takes advantage of the information gained from our analyses up to that point. Using this formula, each arm (or drug) is allocated for the next patients to be enrolled in the  $j^{\text{th}}$

arm proportional to  $V_j^* = \sqrt{\frac{\Pr(U_{jT} = U_{\max,T}) \text{Var}(U_{jT})}{n_{jT} + 1}}$ . This type of allocation tends to have more

desirable properties than simply using  $\Pr(U_{jT} = U_{\max,T})$ . Using this approach will allow us to assign more patients to the most promising arm or drug, and fewer patients to the least promising drug.

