### Missing data:

Our primary statistical inference of the intervention measures (efficacy and medication quit rates) will label all patients with missing VAS data to be imputed as a failure. Therefore our study has valid type I error rates and has nominal confidence interval coverage properties as detailed in the proposal. A patient that is enrolled and randomized (note: after signing the consent form) into the study will either continue to take the randomly assigned pain medication (quit=0) or discontinue (quit=1). Among the patients that continue the pain medication, and have follow-up VAS outcomes, that patient will either drop their VAS pain score by ½ or better (efficacy=1) or they will not (efficacy=0). Among the patients that discontinue treatment of assigned pain medication, or having missing VAS values, they will automatically be recorded as non-efficacious (efficacy=0). Patients that are lost from the study will be considered to have discontinued treatment (quit=1, efficacy =0). The rule above implies that missing data will result in an imputed failure (and hence there are no missing primary outcomes). The primary inference in our study automatically addresses MD-3 of the PCORI Methodology Standards. Note: our secondary statistical inference of the intervention measure of reported VAS changes will be conducted using Bayesian mixed-effect model repeated measures (MMRM) where missing data will be addressed using multiple imputation.

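### Aim 1 asks which drug most improves quality of life, but the readable analysis of SF-12, pain interference, fatigue and sleep is within-arm and names no between-drug contrast

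*Combined protocol and SAP*

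**What the plan says.** Specific Aim 1 in the Abstract is comparative: "Determine which drug is most effective in producing pain relief and improving quality of life in patients with CSPN". Choice of Outcomes lists the scales concerned and defers their analysis to the text after Table 5: "Our secondary endpoints, SF-12, pain interference, fatigue, and sleep disturbance, also will be longitudinally modeled". That text is the Secondary Endpoints section. It names a two-level model (time, patient) and states its purpose as a "hierarchical linear modeling approach to evaluate these variables within each arm across time".

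Two other places bear on the question. The Overview of the Analytic Methods restates the aim without quality of life: "The primary aim of this study is to determine which drug is most effective and most tolerable in producing pain relief". The Missing data section adds a further secondary analysis, but for pain only: "our secondary statistical inference of the intervention measure of reported VAS changes will be conducted using Bayesian mixed-effect model repeated measures (MMRM"; missing values in that analysis go to multiple imputation.

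Two design features matter here. The Background states: "We will not use a placebo group in this comparative effectiveness study". Allocation is adaptive: after 80 patients are enrolled "and equally randomized to the four arms, we begin adapting the randomization", and the aim of the allocation formula is to "assign more patients to the most promising arm or drug, and fewer patients to the least promising drug".

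**The concern.** The aim asks for a ranking of drugs, and the stated analysis describes each drug separately. In a trial with no placebo group, an improvement over three months in one arm contains the drug effect, the placebo response (which the Background itself calls large) and the natural course. Randomization supports the difference between arms, and for these scales no such difference is named.

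A reader can of course lay four curves side by side. That comparison has no interval, and it invites the reading that a drug with a significant within-arm change beats one without. If the contrast is still unspecified when the data arrive, its form could be chosen with the results in view. Adaptive allocation makes that choice less innocent than usual, because the arms will differ in when their patients enrolled. At stake is the quality-of-life part of Aim 1 only.

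**Working it through.** **1. Is a between-drug contrast given anywhere for these scales?**

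| Section | What it covers | Between-drug contrast for SF-12, pain interference, fatigue, sleep |
|---|---|---|
| Choice of Outcomes | Names the four scales, says they will be modelled over time | None; refers onward |
| Overview | Pain relief and tolerability | None |
| Combining Endpoints; Statistical Model | Utility 0.75E + 1 − Q, from pain response and quitting | None; no term for these scales |
| Longitudinal Model | Predicts the 12-week primary outcome from weeks 4 and 8 | None |
| Secondary Endpoints | Two-level model of the four scales | None named; purpose stated as within-arm |
| Missing data | Repeated-measures model for pain change | None; scales not mentioned |

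The documents give no power, alpha or SD for these scales, so there is no planned figure to reproduce.

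**2. Size of the gap.** Four drugs give 4 × 3 / 2 = 6 pairs. If SF-12 alone represents quality of life, 6 comparisons at a given visit are unspecified. If all four scales do, the number is 4 × 6 = 24.

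**3. Why separate within-arm results do not rank drugs (illustration).** Assume the same true change of 0.3 SD in all four arms and a two-sided 0.05 test of change in each. The plan states no such test. With the mean arm sizes n in Table 6, the chance that an arm is significant is p = Φ(0.3√n − 1.96). The chance that at least one arm is significant and at least one is not is 1 − Πp − Π(1 − p). In Scenario 3 (n = 51, 58, 105, 51), p = 0.57, 0.63, 0.87, 0.57, and the result is 81%. Scenarios 1, 2 and 4 give 49%, 77% and 56%. The size depends on the assumed change: 83–88% across scenarios at 0.2 SD and 9–44% at 0.4 SD. Equal drugs can therefore readily look different.

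**4. Enrolment period.** Inputs are the Table 6 mean arm sizes and the first 80 patients split 20 per arm (Bayesian Adaptive Design). The share of an arm enrolled after adaptation starts is (n − 20)/n. If outcomes shift by s SD between the two periods, a pooled contrast that omits period is biased by the difference in shares × s. For the pair with the largest difference:

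| Scenario | Shares | Difference | Bias at s = 0.1 / 0.3 / 0.5 SD |
|---|---|---|---|
| 1 | 79/99 = 0.798 v 77/97 = 0.794 | 0.004 | 0.000 / 0.001 / 0.002 |
| 2 | 96/116 = 0.828 v 31/51 = 0.608 | 0.220 | 0.022 / 0.066 / 0.110 |
| 3 | 85/105 = 0.810 v 31/51 = 0.608 | 0.202 | 0.020 / 0.061 / 0.101 |
| 4 | 89/109 = 0.817 v 42/62 = 0.677 | 0.139 | 0.014 / 0.042 / 0.070 |

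The shift s is assumed; the documents give none. The calculation uses mean arm sizes and treats everyone after the first 80 as one period.

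**The case against.** The strongest reply is that this is a gap in wording. A two-level model can carry arm as a patient-level term, and the figure directly after the Secondary Endpoints text, which is not shown in the available copy, might contain the model equation. Both points stand. They rule out a stronger reading that a reader might infer, namely that the trial will not or cannot compare the drugs on quality of life. The documents neither state nor exclude such a comparison; the readable text simply does not name one.

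Nor do the documents show that the contrast will be picked after the data are seen. The Stakeholders section gives the Steering Committee further development and approval of the protocol, so a contrast could still be fixed in time.

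No section says which instrument measures quality of life. Linking SF-12, or all four scales, to that part of Aim 1 is an inference, which is why the gap is given as 6 or 24.

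The enrolment-period argument is secondary. Nothing in the documents suggests a shift on these scales. Even the largest bias above, 0.11 SD, is a third of the 95% half-width for the same Scenario 2 pair, 1.96 × √(1/51 + 1/116) = 0.33 SD. The start of adaptation is also not fully settled: the Allocation section ties new allocation to evaluation of the stopping rule, which comes later than 80 patients. What stands is that a period term is worth including once a contrast is written, not that its absence is the defect.

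Finally, these endpoints are secondary, and the Overview leaves quality of life out of the primary aim. That limits the consequence but leaves Aim 1 and the analysis at odds.

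**Conclusion.** The point holds for the readable text. Aim 1 poses a comparative quality-of-life question, and the one analysis stated for the candidate scales is within-arm. Followed as written, it would not rank the drugs. The gap is 6 unspecified comparisons on SF-12 or 24 on all four scales, depending on a mapping that the documents leave open. The possible bias from omitting enrolment period is about 0 to 0.11 SD across the four scenarios, under an assumed shift of 0.1 to 0.5 SD and a start of adaptation at 20 patients per arm.

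It would be wrong to infer that the trial's main conclusions are in doubt. Stopping, allocation, and the best-drug and loser decisions use pain response and quitting only and do not depend on these scales. This should be corrected, with medium confidence because of the figure not shown.

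**What to change.** In Secondary Endpoints, state one model per scale, fitted to all four arms, with the month 1, 2 and 3 values as outcomes. Its terms are baseline value, visit, arm, arm-by-visit, enrolment period (one level per randomization schedule) and a random patient effect. Report month-3 between-drug differences with intervals as secondary inference, and keep the within-arm curves as description. Say which scale or scales answer the quality-of-life part of Aim 1. If the missing figure already contains such a model, a sentence naming the contrast and the period term is enough.

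If the sponsor does not want this comparison, label these analyses descriptive and remove the comparative quality-of-life question from Aim 1.

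The first route costs text and a little analysis work; the scales are already collected at baseline and months 1, 2 and 3, so no visit or instrument is added. Its downside is modest precision. Without baseline adjustment, multiplicity adjustment or missing data, 95% half-widths z√(1/n₁ + 1/n₂) across all pairs in Table 6 run from 1.96 × √(1/108 + 1/109) = 0.27 SD to 1.96 × √(1/51 + 1/51) = 0.39 SD. The second route costs wording only.

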### Missing data:

Our primary statistical inference of the intervention measures (efficacy and medication quit rates) will label all patients with missing VAS data to be imputed as a failure. Therefore our study has valid type I error rates and has nominal confidence interval coverage properties as detailed in the proposal. A patient that is enrolled and randomized (note: after signing the consent form) into the study will either continue to take the randomly assigned pain medication (quit=0) or discontinue (quit=1). Among the patients that continue the pain medication, and have follow-up VAS outcomes, that patient will either drop their VAS pain score by ½ or better (efficacy=1) or they will not (efficacy=0). Among the patients that discontinue treatment of assigned pain medication, or having missing VAS values, they will automatically be recorded as non-efficacious (efficacy=0). Patients that are lost from the study will be considered to have discontinued treatment (quit=1, efficacy =0). The rule above implies that missing data will result in an imputed failure (and hence there are no missing primary outcomes). The primary inference in our study automatically addresses MD-3 of the PCORI Methodology Standards. Note: our secondary statistical inference of the intervention measure of reported VAS changes will be conducted using Bayesian mixed-effect model repeated measures (MMRM) where missing data will be addressed using multiple imputation.

## **E. Stakeholders**

The key stakeholders for the PAIN-CONTRoLS project are patients with Cryptogenic Sensory Polyneuropathy (CSPN), their families who cope with loved ones struggling with pain on a daily basis, providers who treat these patients, scientists involved in this study, patients' local and national associations (the local and national chapters of the Neuropathy Association), and ethicists working in healthcare in general and pain management in particular. We already have engaged a number of critical stakeholders—including in discussions of study design, for feedback on measures to be used, and for support for recruitment and completion of the proposed study. Indeed, the decision to propose this study and how it will proceed are a direct result of working with patients and tracking their symptoms. Our patients made it very clear that a rigorous comparative effectiveness study is desperately needed. The organizational

framework we present in Figure 3 visually demonstrates our commitment to inform our research with patient, caregiver, and consumer input at every level. Bold/underlined text in Figure 3 indicates that activity or membership includes patients and other stakeholders (see Engagement

Activities text below for details.)

**Figure 3. Organizational Structure for Stakeholder Engagement**

**Engagement Activities: Researcher and Technical Expert Collaboration**

Our engagement activities began over a year ago. We had an initial brainstorming meeting with approximately 30 researchers and staff at the *Personalized Medicine and Outcomes Center* within the NIH CTSA supported *Frontiers: Heartland Institute for Clinical and Translational Research* program in May 2012. We presented our initial concept of a comparative effectiveness study for painful neuropathy and received outstanding feedback. They advised that we should develop the study so that it most closely resembles real world activity and decision-making between physicians and patients in the **management** of neuropathy pain. This influenced us a great deal in deciding on the design to r **Safety Committee** ts to drugs that are currently given routinely, but for which there have been no systematic studies for use in CSPN. We also were mindful to design the study to dispense these drugs as they would be advised by their doctor—for example, one or two or three times a day, and not try to create a common time or strict number of pills dispensed for each drug. [name] heard [name], talk about adaptive design models for clinical trials at a CTSA meeting in the spring of 2012, and this led to [name] joining the study development team as a consultant.

The **Data and Safety Monitoring Board** (DSMB) will be chaired by [name], Professor of Neurology at Harvard Medical School. Other members of the DSMB will be [name]

[name], MD at Ohio State University, a peripheral nerve specialist; [name] MD, a multiple sclerosis and clinical trials expert at UT Southwestern Medical Center in Dallas; [name], co-director of our CTSA's *Community Partnership for Health* program, [name]; and [name] PhD, a biostatistician from a non-participating academic institution. The DSMB will meet via phone 3-4 times a year to review the status of the study and to make decisions about study continuation. After each meeting, they will prepare a letter that will be disseminated to all members of the PAIN-CONTRoLS Steering Committee and to each participating site. By including all members of the Steering Committee, we ensure that information will be available to our patient Committee members and if appropriate will be included in Newsletter and other communications.

While we will have this official Data and Safety Monitoring Board (DSMB), we also will have a physician safety monitor, [name], who will chair a **Safety Committee** to discuss issues regarding side effects and adverse events in real time as they happen. This is standard for clinical trials. Our Safety Committee will have at least one patient with CSPN as a member, and at least one physician who is not associated with the study. Together they will assess side effects as they occur and make determinations regarding particular patient safety issues. They will provide this information to the study PI and Co PIs and the official DSMB.

The last committee we have previously referred to but did not detail is the PAIN-CONTRoLS **Steering Committee**. The Steering Committee is made up of the following: at least one representative from the Patient Advisory Board, [name] MD, PI, [name] MD, [name] MD, [name] MD, [name] MD, [name] MD, [name] MD, [name] MD, [name] PhD, statistician, [name] from *the Center for Practical Bioethics*, and [name] PhD, representing the community engagement function for Frontiers (CTSA grant at KUMC). Because we actively involved patients in developing the PAIN-CONTRoLS project, several have already agreed to serve on the Steering Committee. The Steering Committee will oversee additional development of the protocol and execution of the study. They will approve the final protocol before it is distributed to each site, and will be kept up to date on reports from the Data and Safety Monitoring Board. They also may ask the DSMB to convene for review of safety issues at any time.

The Steering Committee will review all manuscripts and presentations prepared about the PAIN-CONTRoLS project and using data from this project. The patient member of the Steering Committee will be charged with ensuring these are shared with the full Patient Advisory Board. The Steering Committee also will ensure that each site investigator maintains contact with their local chapter of the Neuropathy Association (if one exists near their site) and visits or sends a representative to the local chapter meetings several times a year.

We are committed to conduct this project in the most transparent way possible, seeking meaningful communication with and participation by all of our stakeholders. In particular, patients and other stakeholders have been fully integrated into the planning and the design of this project and all will be actively involved in the conduct of this study and the dissemination of findings from this study. Patients and other stakeholders sit on every committee, and a patient will co-chair the important Communications Committee.

KUMC intends to utilize a "remote or virtual" monitoring plan for this trial. The goal with remote monitoring is to help site investigators and research staff with the prevention or mitigation of important and likely risks to data quality, protection of human subjects and trial integrity.

The remote monitor will ask for copies of signed consent forms and other source documents to verify legal informed consent, subject eligibility and outcome measures entered into the database. We will try to request remote monitoring 2-3 subjects per site at random. Completion and accuracy of subject eligibility, the Likert Pain Scale, the NIH Pain Interference

Scale, the NIH Fatigue Interference Scale, NIH Sleep Disturbance Scale, SF-12 and adverse event reporting will also be verified during remote monitoring.

Each site will be asked to send protected documents containing individually identifiable personal and/or health information through KUMC's secure portal called Secure File Transfer Network.

The project managers will monitor the database and to confirm that all data has been entered on a weekly basis. They will report to [name] if they identify a site that is unable to enter data in a timely manner.

